### **8.6 Prior and Concomitant Therapy**

All concomitant medications will be collected. Prior corticosteroid therapy will be collected as well. All concomitant medications except for steroids are permitted during the study.

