## 2 Brief Summary of Research

Diamond Blackfan anemia (DBA) is a rare inherited pure red cell aplasia. The two main non-stem cell transplant therapeutic options are corticosteroids and red blood cell (RBC) transfusions. About 80% of DBA patients initially respond to corticosteroids, however, half of the patients cannot continue due to side effects or loss of response. These patients are then typically dependent on RBC transfusions throughout life. Each of these treatments is fraught with many side effects and significant morbidity and mortality are potential consequences of hematopoietic stem cell transplantation (SCT). The majority of individuals with DBA have mutations in genes encoding structural proteins of the small or large ribosomal subunit leading to deficiency of the particular ribosomal protein (RP). Studies in zebrafish with RP deficiencies confirmed the association between RP defects, p53 activation and the appearance of a DBA phenotype. Using the RP deficient zebrafish embryo model, high throughput drug screens have demonstrated a strong hematologic response to several calmodulin inhibitors. One of these chemicals is trifluoperazine (TFP). TFP treatment of a mouse model of DBA also increased the red blood cell count and the hemoglobin (Hb) levels in the mice. TFP is a FDA-approved typical antipsychotic agent that has been available since 1958 with a well-known safety profile. In the United States, TFP is approved for the short-term treatment of generalized non-psychotic anxiety; treatment or prevention of nausea and vomiting of various causes; and, management of psychotic disorders.

In this study we aim to determine the safety and tolerability of TFP in adult subjects with DBA, as a prelude to a possible proof of concept (PoC) trial (as a separate study). TFP's expected dose-limiting toxicity is primarily neurologic (extrapyramidal) when used long-term at typical anti-psychotic doses (range 10-50 mg daily). Non-neurologic adverse effects in

subjects with DBA have not been investigated. We will perform a dose escalation study to define the safety and tolerability of lower doses of this agent in subjects with DBA.

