This class of drugs has not been tested specifically in subjects with DBA prior to this study. To mitigate the potential risks of administering TFP to this new population, we will (1) start dosing at dose levels well below those prescribed for psychosis over the past several decades, (2) dose escalate to a maximum of 10 mg daily (the lowest dose typically prescribed for psychosis), and (3) perform weekly safety monitoring. Given the positive signal in DBA animal models and the 60-year clinical experience with higher doses of TFP, this drug warrants a trial in humans to assess tolerability in DBA. If tolerated, this trial will support either a PoC trial of low-dose TFP in DBA, or the advancement of a chemically modified TFP-like drug (to alleviate the neurologic toxicity) for the treatment of DBA.

This is a dose escalation safety and tolerability study to evaluate the presence of TFP-related adverse events in DBA subjects, and to determine the maximum tolerated dose (MTD) of TFP in DBA. The dose escalation strategy is described in [Section 3.5 Dose Rationale and Risk/Benefits](#).

Some first-in-human (FIH) trials may implement an enrollment restriction rule such that two subjects are dosed in a given cohort, and a third subject is not dosed until both of the first two subjects have demonstrated tolerability. For this trial, we have elected not to use such an enrollment restriction design for the following reasons:

- a. This is not a FIH trial: TFP has been in wide clinical use for 60 years.
- b. Our dose levels (1 mg daily, up to max 10 mg daily) are all well within and below the safe range of clinical use. Doses in the 2-6 mg daily range have been shown to have a side effect profile similar to placebo in patients with anxiety ([Mendels, 1986](#)). A randomized clinical trial comparing TFP 15 mg/day vs. placebo in schizophrenic subjects revealed no difference in the rates of severe adverse effects, Parkinsonism or dystonia compared to placebo (Koch, 2014). Doses for psychosis range from 10 mg daily up to 40-50 mg daily, whereas we will dose at 1, 2, 5, and 10 mg daily only.

- c. We will monitor for safety, specifically for any hematologic toxicity and for extrapyramidal/central nervous system (CNS) effects. Dose escalation criteria and actions, as well as subject and cohort stopping rules are detailed in [Section 6 Study Design](#).

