## **3.2 *Investigational Agent - Trifluoperazine***

### **3.2.1 Description**

TFP is a piperazine phenothiazine antipsychotic with 5 mg orally equivalent to 100 mg of oral chlorpromazine, the prototype antipsychotic. TFP is a typical antipsychotic of the phenothiazine chemical class that has been used for the treatment of psychiatric subjects since 1958 ([Rudy, 1958](#)). TFP acts as a dopamine antagonist with antipsychotic and antiemetic activities. TFP blocks CNS postsynaptic mesolimbic dopaminergic D1 and D2 receptors and depresses the release of hypothalamic and hypophyseal hormones and the reticular activating system, thus affecting basal metabolism, body temperature, wakefulness, vasomotor tone, and emesis. In the United States, trifluoperazine hydrochloride tablets, USP, are approved for the short-term treatment of generalized non-psychotic anxiety; treatment or prevention of nausea and vomiting of various causes; and management of psychotic disorders. In part because of its side effect profile, TFP has been largely replaced by second and third generation antipsychotic medications. It is associated with an increased risk of death in elderly subjects treated for dementia-related psychosis. Nevertheless, TFP remains commercially available worldwide and the risks attendant to its use are well understood and generally manageable.

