## 7.2 Exclusion Criteria

Subjects who meet any of the following criteria will not be eligible to participate in the study:

1. Liver: aspartate aminotransferase (AST) > 5 x the upper limit of normal (ULN), alanine aminotransferase (ALT) >5 x ULN, or bilirubin > 5 x ULN.
2. Heart disease (New York Heart Association classification of  $\geq 3$ ; Appendix F).
3. History of angina.
4. Uncontrolled hypertension. If hypertension is considered clinically stable, systolic blood pressure must be <150 mmHg or diastolic blood pressure must be <100 mmHg.
5. Subjects currently responsive to corticosteroids for treatment of DBA.
6. Treatment with another investigational drug or device <56 days pre-study entry. Subjects who participated in an earlier cohort of this trial may participate in a subsequent cohort if (a) they meet all eligibility criteria, (b) did not experience any adverse effects  $\geq$  Grade 3 while on TFP, and (c) discontinued TFP  $\geq$  6 days (10 half-lives) prior to day 1 of the subsequent cohort.
7. Pregnant or lactating females.
8. Any history of severe allergic reaction requiring the use of epinephrine.
9. Known hypersensitivity to the study drug or other phenothiazines.
10. History or presence of extrapyramidal signs.
11. History of cancer.

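### Section 8.6 permits every concomitant drug except steroids, so another dopamine antagonist, or a drug that suppresses extrapyramidal signs, can blur the toxicity reading at any dose level

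*Combined protocol and SAP*

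**What the plan says.** The rule on co-medication is in section 8.6: "All concomitant medications except for steroids are permitted during the study". Concomitant drugs are otherwise only collected.

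Three exclusions in section 7.2 come near the issue:

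- Exclusion 9 reads "Known hypersensitivity to the study drug or other phenothiazines". It concerns allergy, not current use.
- Exclusion 10 reads "History or presence of extrapyramidal signs". It concerns signs, not the drugs that cause or suppress them.
- Exclusion 6 covers other investigational products within 56 days. It lets a subject from an earlier cohort return if TFP was stopped at least "6 days (10 half-lives) prior to day 1 of the subsequent cohort".

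The pharmacology is described elsewhere. Section 3.2.1: "TFP acts as a dopamine antagonist with antipsychotic and antiemetic activities". Section 2 says that TFP's "expected dose-limiting toxicity is primarily neurologic (extrapyramidal) when used long-term at typical anti-psychotic doses", and lists among the risk mitigations that the trial will "dose escalate to a maximum of 10 mg daily (the lowest dose typically prescribed for psychosis"). Section 3.5 ties the cap to side effects that rise with dose and plasma level.

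Section 15.4 acts on extrapyramidal symptoms without a grade threshold. One affected subject stops treatment. If more than one subject is affected, the trial stops. In Cohorts B, C and D the MTD is then set one dose lower, and in Cohort A none is declared.

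**The concern.** The protocol expects the limiting toxicity to be extrapyramidal, caps the dose to keep it rare, and stops on it at any grade. Yet it expressly allows other drugs that act on the same system, in either direction.

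A second dopamine antagonist makes the subject's total blockade higher than the assigned dose implies. An extrapyramidal event then cannot be cleanly assigned to the TFP dose, and the cap limits only the study tablets. A drug that suppresses extrapyramidal signs works the other way: the event may not appear, and an event that does not appear cannot trigger 15.4.

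There is no control arm, and each dose decision rests on 3 to 6 subjects. One such subject can therefore matter to whether a dose is passed or rejected.

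**Working it through.** **1. Is the restriction found elsewhere?** None of the 10 inclusion and 11 exclusion criteria bars current use of the drug classes in question. Exclusion 5 concerns response to corticosteroids, and exclusions 6, 9 and 10 are described above. Sections 9.1 to 9.5 review or record treatments but prohibit none. Section 8.6 is the operative rule, and it permits them.

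**2. The plan's own washout.** Section 3.2.2 gives a TFP half-life of 12.5 h, and section 3.5.1 gives about 12 to 14 h.

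- 10 x 12.5 h = 125 h = 5.2 days
- 10 x 14 h = 140 h = 5.8 days

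Both agree with the 6 days in exclusion 6(c). The plan therefore guards against residual TFP from an earlier cohort, but not against a full concurrent dose of an equivalent drug.

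**3. Added blockade.** Section 3.2.1 equates 5 mg oral TFP with 100 mg oral chlorpromazine, so 1 mg TFP corresponds to 100/5 = 20 mg chlorpromazine. Assume that doses add.

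| Cohort | TFP, mg/day | Chlorpromazine to reach the next cohort's dose | Chlorpromazine to reach 10 mg-equivalent |
|---|---|---|---|
| A | 1 | (2 - 1) x 20 = 20 mg/day | (10 - 1) x 20 = 180 mg/day |
| B | 2 | (5 - 2) x 20 = 60 mg/day | (10 - 2) x 20 = 160 mg/day |
| C | 5 | (10 - 5) x 20 = 100 mg/day | (10 - 5) x 20 = 100 mg/day |
| D | 10 | no higher cohort | 0, so any amount passes it |

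In Cohorts A and B a small added dose mainly blurs the dose level. The cap itself is at issue mainly in C and D. In Cohort D, 100 mg/day gives 10 + 100/20 = 15 mg-equivalent.

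**4. Masking.** The cohort-level rule in 15.4 needs two affected subjects. With three subjects there are 3 possible pairs. If one subject's signs are fully suppressed, only 1 pair remains: both of the others must be affected. With six subjects the pairs fall from 15 to 10. These are counts, not probabilities.

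**5. Attribution.** Section 15.4 lists extrapyramidal symptoms, then SAEs and events of Grade 3 or higher, then a phrase requiring a judged causal link to TFP. That phrase may qualify the whole list or only its last items.

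- If it qualifies the whole list, the investigator must divide causality between two dopamine antagonists in one subject.
- If it does not, an event driven by the other drug counts fully against the TFP dose.

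Co-medication spoils the reading either way. The start of the cohort rules in section 6.1 is missing from the text available to me, so I make no claim on whether 6.1 counts only related events.

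**6. Time covered.** Section 15.4 has no 21-day limit, and section 15.1 records adverse events until 7 days after the last dose. Appendix A and section 9.5 schedule no recording of concomitant therapy at Visit 4. A suppressing drug started in that last week would be neither barred nor scheduled for recording.

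**7. Screening window.** Ten half-lives fit into 28 days only if the half-life is at most 28 x 24/10 = 67.2 h. For longer-acting drugs, earlier use must be asked about.

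**The case against.** The strongest reply is that the size of the problem is unknown and may be small. The documents give no usage rate for these drugs in adults with DBA. Section 3.4 reports that at 15 mg/day TFP the rates of severe adverse effects, Parkinsonism and dystonia did not differ from placebo, although akathisia was more frequent. By the equivalence above, a Cohort D subject would need 100 mg/day chlorpromazine just to reach that level, and exposure lasts only 21 days. Section 3.2.1 does not say that its equivalence holds for extrapyramidal risk, and additivity is an assumption. All of this stands and limits the severity.

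The masking route is also narrower than it first looks. Exclusion 10 removes anyone who was given a suppressing drug because of extrapyramidal signs. What remains is preventive use, or use for another reason. That such drugs suppress signs is general pharmacology; the documents do not state it. The pair counts assume complete suppression.

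There are safeguards: neurological examination at Screening and Visits 1 to 3, and at Visit 4 under Appendix A; recording of concomitant drugs at Visits 1 to 3; causality assessment; medical-monitor review; and discontinuation at the investigator's discretion. None of them keeps a co-medicated subject out of a cohort, and an examination cannot show a sign that has been suppressed.

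Two stronger readings are tempting, and the documents do not support them.

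- Section 2 notes that "TFP is approved for the short-term treatment of generalized non-psychotic anxiety; treatment or prevention of nausea and vomiting of various causes", so a reader might infer that 8.6 lets a subject take marketed TFP on top of the study tablets. Section 3.5 caps the TFP given to these subjects at 10 mg and section 6.1 defines cohorts by daily TFP dose, so extra TFP already conflicts with the plan.
- Section 10 lists interactions with CNS depressants and atropine, and a reader might take this as evidence for the present point. Those entries describe stronger or longer action of the other agents. They describe neither added dopamine blockade nor masking.

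**Conclusion.** The point holds in a limited form and should be fixed. Section 8.6 is an express permission, not a missing detail. Followed as written, it admits drugs that can confound or hide the toxicity that the protocol expects to be dose-limiting and on which 15.4 acts.

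The only supportable measure of size is the set of thresholds: 20, 60 or 100 mg/day chlorpromazine moves a Cohort A, B or C subject to the next dose level, and any amount exceeds 10 mg-equivalent in Cohort D. They rest on the protocol's equivalence and on additive doses.

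A reader might infer that the declared MTD is likely to be wrong, or try to compute how masking changes the chance of escalation. Either would need event rates, usage rates and a degree of suppression, and the documents give none of these. Confidence is high on the gap in the text and moderate on its practical importance.

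**What to change.** Amend 8.6, with a matching exclusion in 7.2, to prohibit:

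- other phenothiazines, antipsychotics and dopamine antagonists;
- drugs that suppress extrapyramidal signs, for example centrally acting anticholinergics, whatever the reason they are taken.

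Give a short named list with half-lives. The ban runs from 10 half-lives of the drug concerned before Day 1, the interval that exclusion 6(c) uses for TFP, to the end of adverse event recording 7 days after the last dose. Check the list in the prior-treatment review already done at Screening, asking further back for drugs with half-lives above about 67 h. Record concomitant drugs at Visit 4 as well.

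No needed drug is stopped for the trial:

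- A subject who needs a listed drug before entry is not enrolled.
- A subject who must start one on study stops TFP, stays in the safety analysis, and is replaced for the cohort decision unless a counted event has already occurred.
- Rescue treatment of an extrapyramidal event is allowed once the event is recorded and counted.

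The cost is one protocol amendment and the loss of some otherwise eligible subjects with a rare disease, number unknown. The cohort arithmetic in 14.1 (4 x 6 = 24 at most, 3 at least) is unchanged for subjects who count toward cohort decisions. Because a replaced subject adds to the number enrolled, 14.1 should say that its maximum refers to those subjects.

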### **8.7 Packaging**

TFP is to be dispensed in a tight, light-resistant container, as defined in the USP, using a child-resistant closure. The subject will receive a 21 day supply of 1 mg or 5 mg tablets. The label for TFP will include the institution name, address and telephone number, the protocol number, drug name, dosage form and strength, amount of drug per container, lot number, expiration date, medication identification, dosing instructions, storage conditions, and required caution statements and/or regulatory statements as applicable. Additional information may be included on the label as applicable per local regulations.

### **8.8 Blinding of Study Drug/Device**

There is no blinding of the study drug in this study.

### **8.9 Receiving, Storage, Dispensing and Return**

#### **8.9.1 Receipt of Drug Supplies/Device**

Upon receipt of the study drug, an inventory must be performed and a Drug Receipt Log filled out and signed by the person accepting the shipment. It is important that the designated study staff counts and verifies that the shipment contains all the items noted in the shipment inventory. Any damaged or unusable study drug in a given shipment will be documented in

the study files. The investigator must notify study sponsor of any damaged or unusable study drug that were supplied to the investigator's site.

### **8.9.2 Storage**

TFP tablets are to be stored at 20° to 25°C (68° to 77°F) in the study pharmacy.

### **8.9.3 Dispensing of Study Drug**

The subject will be dispensed a 21 day supply of 1 mg or 5 mg tablets based on Dose Level 1, 2, or 3 and 4, respectively. The subject will receive study drug once during this study.

### **8.9.4 Return or Destruction of Study Drug**

At the completion of the study, there will be a final reconciliation of drug shipped, drug consumed and drug remaining. This reconciliation will be logged on the drug reconciliation form, signed and dated. Any discrepancies noted will be investigated, resolved, and documented prior to return or destruction of unused study drug. Drug destroyed on site will be documented in the study files.

## **9 Study Procedures (Screening and Visits 1-4)**

Please see Appendix A for a Schedule of Study Assessments.

### **9.1 Screening**

The Screening Period is from Day -28 to Day -1 prior to the subject starting the study drug on Day 1 of the study. If consent was not previously obtained by mail then the PI will obtain informed consent at a Screening visit. If the consent was obtained by mail then the consent will be reviewed again with the subject at the initial visit. The subject will be then be assessed for inclusion and exclusion criteria with a review of his/her medical record, including prior treatments, procedures, and transfusion history (for the previous 12 weeks at least). A physical examination including height at 1st visit, weight, vital signs, blood pressure and neurological exam will be performed on the subject. Karnofsky performance status will be assessed. Blood work will be performed for a complete blood count (CBC; RBC count, hemoglobin, hematocrit, absolute reticulocyte count, white blood cell count, absolute neutrophil count, and

platelet count), serum chemistry panel for hepatic and renal function (blood urea nitrogen, creatinine, bilirubin [total and direct], aspartate aminotransferase [AST], and alanine aminotransferase [ALT]). If the subject is a female, then menstrual status will be assessed and a serum pregnancy test will also be performed. If all the criteria are evaluated and subject is confirmed to start the study, Screening and Visit 1 may be combined into one visit and the Screening blood work can be used as the Visit 1 blood work if within  $\pm$  1 day.

## **9.2 Visit 1**

Visit 1 will be Day 1 of the study and will be the day that the subject starts the study drug. If Screening assessments were completed the day before then the subject's physical examination and blood work results can be used for Visit 1 as well. A physical examination including height at 1st visit, weight, vital signs, blood pressure and neurological exam will be performed on the subject. Karnofsky performance status will be assessed. Blood work will be performed for a complete blood count (CBC; RBC count, hemoglobin, hematocrit, absolute reticulocyte count, white blood cell count, absolute neutrophil count, and platelet count), serum chemistry panel for hepatic and renal function (blood urea nitrogen, creatinine, bilirubin [total and direct], aspartate aminotransferase [AST], and alanine aminotransferase [ALT]). If the subject is a female, then menstrual status will be assessed and a serum pregnancy test will also be performed. Blood for pharmacodynamic marker analysis will be collected, if applicable (Appendix J). All concomitant therapies will be documented. The subject will be dispensed a 21-day supply of the study drug once all evaluable criteria are met and will start the study drug on Day 1. Visit 1 should occur within 7 days following a blood transfusion.

## **9.3 Visit 2**

Visit 2 will be Day 11 ( $\pm$  1 day) of the study. The subject will undergo full safety analysis, including a physical examination (including weight, vital signs, blood pressure and neurological exam). Karnofsky performance status will be assessed. Blood work will be performed for a complete blood count (CBC; RBC count, hemoglobin, hematocrit, absolute reticulocyte count, white blood cell count, absolute neutrophil count, and platelet count), serum chemistry panel for hepatic and renal function (blood urea nitrogen, creatinine, bilirubin [total and direct], aspartate aminotransferase [AST], and alanine aminotransferase [ALT]), and

pharmacodynamic marker analysis, if applicable (Appendix J). If the subject is a female, menstrual status will be assessed and a serum pregnancy test will also be performed. Transfusion history will be documented. The subject will be questioned and evaluated for any adverse events. All concomitant therapies will be documented.

#### **9.4 Visit 3**

Visit 3 will be Day 22 ( $\pm 2$  days) of the study. The subject will undergo full safety analysis, including a physical examination (including weight, vital signs, blood pressure and neurological exam). Karnofsky performance status will be assessed. Blood work will be performed for a complete blood count (CBC; RBC count, hemoglobin, hematocrit, absolute reticulocyte count, white blood cell count, absolute neutrophil count, and platelet count), serum chemistry panel for hepatic and renal function (blood urea nitrogen, creatinine, bilirubin [total and direct], aspartate aminotransferase [AST], and alanine aminotransferase [ALT]), and pharmacodynamic marker analysis, if applicable (Appendix J). If the subject is a female, menstrual status will be assessed. Transfusion history will be documented. The subject will be questioned and evaluated for any adverse events. All concomitant therapies will be documented.

